10.9 Data Analysis

Primary analyses will use an intent-to-treat paradigm, wherein all randomized subjects are included according to their randomized treatment assignment, regardless of actual treatment received, protocol violations, etc. for the primary outcome. The data will be summarized using descriptive statistics for continuous variables (mean, standard deviation, number of observations, and percentiles) and frequency statistics (frequencies and percentages) for categorical variables. All hypothesis tests will be two-sided and all analyses will be performed using SAS software, (SAS Institute, Inc., Cary, NC) or R (open source).

Primary efficacy analysis will be done using a logistic regression model to compare the two treatment arms with respect to the primary outcome of a good birth outcome while adjusting for recruitment site and baseline BMI. The proportion of good birth outcomes in each treatment

arm will be reported, as well as the odds ratio (OR) and corresponding 95% confidence interval (CI). We propose a number of secondary analyses and acknowledge that the power of our study may be low for some of these outcomes. However, even if not significant, examination of these secondary endpoints will guide future research in the area of infertility treatment. Logistic regression models will be fit to binary outcomes, such as pregnancy status (yes/no), to assess differences in the treatment arms while adjusting for recruitment site and baseline BMI. For rare binary events, e.g., multiple pregnancy births or other adverse events, Firth's penalized likelihood approach to logistic regression will be used to address the issue of having a small number of events.⁹⁰ Effect sizes from the logistic regression models will be quantified using the OR and 95% CI.

The analysis of other secondary outcomes will entail the application of statistical methods that have been developed for correlated data since repeated observations will be made over time on each individual, and these methods allow for both within-group and between-group comparisons to be assessed. For secondary outcomes such as weight loss or ultrasound parameters, a linear mixed-effects model will be fit where the main independent variables will be treatment arm, cycle number, and their interaction, as well as the randomization stratification factors of recruitment site and baseline BMI as covariates.⁹¹ The linear mixed-effects model is an extension of linear regression that accounts for the within-subject variability inherent in longitudinal trials and has the flexibility to adjust for potentially confounding covariates if deemed necessary. Potential additional covariates in the models may include prior exposure to study medication, the baseline value of the outcome, and age. The effect size will be quantified from the mixed-effects models using the difference in the means between the treatment arms and corresponding 95% CI. For binary outcomes measured over time, e.g., ovulation rates, generalized estimating equations with a logit link, an extension of logistic regression that accounts for correlated data, will be fit where the main independent variables will be treatment arm, cycle number, and their interaction, as well as the randomization stratification factors of recruitment center and baseline BMI as covariates.⁹² Cox proportional hazards models and the Kaplan-Meier method will be applied to compare time to pregnancy and time to live birth in the treatment groups.

Participant Drop-out and Other Missing Data: While every attempt will be made to collect complete data and prevent drop-out, missing data are inevitable. The sample size has been inflated by 20% in anticipation of some drop-out such as participant retention issues (based on experience in the PPCOS I, PPCOS II, OWL PCOS, and AMIGOS studies). The mechanism for missing data (missing completely at random, missing at random, or missing not at random) will be examined prior to beginning the analyses. We will compare the available characteristics of those with missing data to those with complete data and attempt to predict missingness with available data using multiple logistic regression and calculating the area under the receiver operating characteristic curve.⁹³ If necessary, imputation techniques may be used,⁹⁴ and shared parameter models or random pattern-mixture models considered if the preliminary analyses suggest that the data are missing not at random so that individuals with missing data can be included in the analyses.

Statistical versus Clinical Significance and Multiple Testing: As our analyses are based upon defined hypotheses, we have not included corrections for multiple testing. While the issue of p-value adjustment for multiple testing has long been a topic of discussion in observational

epidemiology and clinical trials, it generally is accepted that p-values should not be the sole criterion for assessing relationships. Conclusions will be based on the preponderance of scientific evidence related to each hypothesis, considering point estimates and confidence intervals, as well as statistical significance. Nonetheless, findings with marginal statistical significance will be interpreted cautiously, taking into consideration whether multiple testing could have contributed to a type I error.

11 Data Collection, Site Monitoring and Adverse Experience Reporting

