1.5 Treatment

The intensive lifestyle modification intervention will consist of caloric restriction (consumption of approximately 1200-1500 kcal/d) centering around the use of meal replacements (Nutrisystem), use of an over-the-counter weight loss medication (Alli, which is brand name Orlistat, a gastric lipase inhibitor which limits gut fat absorption), and increased physical activity (goal of reaching 10,000 steps a day). The pretreatment intervention will last 16 weeks and is designed to promote a weight loss of approximately 7% of total body weight in the intensive group. Women in the standard lifestyle intervention (standard) will receive publicly available written materials that promote engagement in increased physical activity. Detailed instruction of physical activity will not be provided. Participants in both groups will receive activity tracking devices (Fitbit Wireless Activity Tracker) and wireless scales (Fitbit Aria Wireless Activity Scale) to promote adherence to the interventions and to allow monitoring for compliance by study personnel. The pretreatment intervention will last 16 weeks. Both groups will aim to build up to 10,000 steps/day with a recommendation to increase steps from baseline by 500 steps/per week. We will monitor subjects monthly during this preconception intervention. All subjects randomized will receive after 16 weeks of lifestyle modification, regardless of adherence or

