1.8 Statistical Analysis

The primary analysis will use an intent-to-treat approach examining differences in the good birth outcome rate in the two treatment arms. The study is powered with 80% power and an alpha of 0.05 to detect an absolute 15% difference in good birth outcome (a live birth of an infant born at ≥ 37 weeks, with a birth weight between 2500 and 4000g and without a major congenital anomaly) between the two treatment groups. We project the proportion of good birth outcomes to be 0.25 in the standard lifestyle group and 0.40 in the intensive lifestyle group. The sample size is inflated to reflect a 20% dropout rate, giving us 190 subjects in each group. A logistic regression model will be fit to compare the treatment arms with respect to the primary outcome of good birth outcome while adjusting for the randomization stratification factors of study site and baseline BMI. The analysis of other secondary (supplemental) outcomes measured over time will entail the application of statistical methods that have been developed for correlated data since repeated observations will be made over time on each individual. For secondary outcomes such as weight loss, a linear mixed-effects model will be fit where the main independent variables will be treatment group, time, and their interaction as well as the randomization stratification factors as covariates. Logistic regression models will be used in secondary analyses to evaluate the predictive value of treatment arm, clinical site, prior exposure to ovulation induction drugs, age, and other explanatory variables on binary outcomes

(e.g., singleton live birth, abortion). Cox proportional hazards models and a Kaplan-Meier method will be applied to compare time to pregnancy in the treatment groups.

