- Collect urine and blood sample for RMN Biologic Repository if consent is signed
- Collect saliva sample if consented

7. Distribute Testing and Study Supplies
 - a. Distribute salivary collection kit, if consented.

Randomization Visit:

Randomization visit can take place regardless of menstrual cycle day and as soon after screening visit as subject and couple meet inclusion/exclusion criteria. Subjects will be informed in person of their randomization assignment. This is to allow for in person counseling of the lifestyle modification and answer face to face any concerns about their treatment assignment. Subjects will undergo during this visit: extensive orientation to the goals of the lifestyle modification, dispensing of all supplies and medications, and review of tracking and self-reporting requirements.

1. Perform limited physical exam, including weight and vital signs.
2. Orient subject to study treatment group including activity recommendations and use of meal replacements and orlistat.
3. Dispense study supplies such as Aria Wifi scale and Fitbit Activity tracker.
4. Dispense weight loss medication (orlistat) and provide instructions for ordering meal replacements on Nutrisystem’s website to subjects randomized to the extensive lifestyle modification arm.
5. Dispense intercourse and menstrual diaries.
6. Prenatal vitamins with folic acid dispensed.
7. Collect central core blood specimen as well as urine and blood reserve sample for ancillary studies (to be stored on site) (with consent). This will include hormonal assays for sex steroids (E2, P4, Testosterone), other reproductive hormones (SHBG), adipokines (leptin, adiponectin) and other hormonal and metabolic parameters that are determined relevant to the study.

8. Collect blood for DNA for the pharmacogenomic studies (with consent) to be stored on site.
9. Collect all available biospecimens from subject and male partner for RMN Biologic Repository (with consent).
10. Collect saliva specimen (with consent).

Monthly Visit during Lifestyle Modification Phase (Phase 1) (N = 3)

1. Perform limited physical exam, including weight, waist circumference, and vital signs (respiratory rate, pulse, and blood pressure).
2. Perform urine pregnancy test.
3. Collect menstrual and intercourse diaries, dispense new for next month.
4. Collect remaining study medications and perform pill count.
5. Dispense study supplies and medications, Prenatal vitamin, if applicable, orlistat.

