6. Ensure that meal replacements for the next month have been ordered through Nutrisystem.
7. Collect adverse events.
8. Collect blood and urine reserve sample for ancillary studies (to be stored on site) and central core specimens which will be run at a core lab facility.
9. During the 3rd monthly visit, dispense saliva kit for collection to be returned Phase 1 closeout, if consented.

Lifestyle Modification Closeout Visit (Week 16)

Subjects will undergo a repeat baseline visit at the end of their 16 week lifestyle modification phase. This will again be independent of cycle day. We will not repeat breast and pelvic exam, pap smear or other items required for inclusion in the study that were obtained at the baseline or screening visits. Intercourse and menstrual diaries will be collected. Female study participants will have a limited physical exam. We will defer transvaginal ultrasound exam until the baseline visit of the infertility treatment cycle. We will obtain questionnaires and biospecimens.

1. Perform limited physical exam, including weight, waist circumference and vital signs (as above).
2. Perform urine pregnancy test.

3. Collect menstrual and intercourse diaries.
4. Collect remaining study medications and perform pill count.
5. Collect adverse events.
6. Collect blood and urine reserve sample for ancillary studies (to be stored on site) and central core specimens which will be run at a core lab facility. Collect specimens for repeat safety screening (Table 8).
7. Collect saliva sample.
8. Repeat full screening visit including hirsutism and acne scoring, QOL questionnaires (excluding DHQII) (See above screening visit) with the exception of full physical exam and transvaginal ultrasound (which will be performed at the start of the subsequent infertility treatment baseline visit).

Baseline Ultrasound Visit for Empirical Infertility Treatment (Phase 2)

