This baseline visit will be performed at the start of Cycle 1 only. The initial dose of clomiphene citrate will be 100 mg/day, which may be adjusted upwards or downward depending on response in subsequent cycles. Women may undergo a total of up to 3 cycles culminating in hCG administration. Subjects may begin subsequent cycles immediately following failed cycles, as long as they meet baseline criteria of a negative urine pregnancy test. Subjects may continue in the study after one failed cycle (i.e. either no development of follicles on study medication). If a subject experiences a second failed cycle, it is recommended to discontinue the subject from the study.

1. Subject will call with menses and come in between days 1-5 of their menstrual cycle (Preferably day 3 for baseline monitoring visit).
2. Check Urine Pregnancy test.
3. Obtain weight.
4. Perform baseline ultrasound. If subject has a cyst with a mean diameter of >30mm, do not continue the visit. Have the subject return with her next menses for a repeat baseline visit.
5. Collect vaginal microbiome and rectal microbiome swab.
6. Dispense Infertility Treatment Study Medication (see Table 9). Please note, if the female has a prior history of over-response to clomiphene citrate at the 100mg dose, the starting dose may be adjusted downward.
7. Obtain central core lab specimens and blood and urine reserve (to be stored on site) for ancillary studies (with consent).

8. Dispense menstrual and intercourse diaries.
9. Schedule Day 8-12 visit for follicular monitoring.

Table 9: Study Medication and Dosing

Protocol	interval	dose	method	start	finish	future cycles
CC	Daily	100 mg	pill	Day 3*	Day 7	Can be started at 50-150 mg/d= (1 to 3 pills)

*(+/- 2 days)

Empirical treatment Cycle Visit number 2:

Within 3 days after completing 5-day drug cycle (Cycle Day 8-12)

1. Transvaginal ultrasound for endometrial and follicular monitoring.
2. Adverse effects and concomitant medications query.
3. During cycle 2 & 3, medication bottles and menstrual diaries from previous cycle will be collected.

Study treatment Cycle visits number 3 and beyond:

Visits for subjects will be conducted on an individualized basis until hCG administration. When a decision has been made to give hCG on the next day, a follow up monitoring visit on that day is unnecessary.

1. Transvaginal ultrasound examination for endometrial and follicular monitoring.
2. Adverse effects and concomitant medications query.

hCG administration day:

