7.3.2 Physical Exam

A physical exam with a standard pelvic and breast exam will be performed on all patients by a study physician. Height, weight and waist and hip circumferences will be recorded to the nearest 0.1 cm, 0.1 kg and 1 cm, respectively. Waist will be measured at the level of the umbilicus and hip circumference will be measured at the widest diameter. Participants will be weighed while dressed in light clothing, without shoes. Weight and waist circumference will be collected at each site visit. Blood pressure will be determined in the right arm in the sitting position, and a large cuff will be used as necessary. Blood pressure will be assessed at each visit. Elevated blood pressures ($\geq 160/100$) will be repeated following acclimation to the study environment. All patients aged 21 and older should have had a normal Pap smear in accordance with current ACOG guidelines⁸⁰; otherwise, one should be performed at the screening exam. Subjects with cytological abnormalities will need to have these resolved prior to study entry.

A hirsutism assessment will be made via the modified Ferriman-Gallwey hirsutism score (**Figure 4**) by trained study personnel⁸¹.

Figure 4: Modified Ferriman-Gallwey Hirsutism Scale

Medscape

An acne assessment will be made by trained personnel using a standard acne lesion assessment (count) diagram and definitions (**Table 10**). Photographic examples of each grade will be provided to investigators as well as training to study personnel. When counting facial acne lesions, it is important that all lesions be counted, both non-inflammatory and inflammatory, examining areas of the forehead, cheeks, and chin and avoiding the nose.

Table 10: Acne Grading Method

Name	Description
Open Comedone (Blackhead)	Results when residual skin oil, makeup, dirt, dead skin, and small hairs impact a sebaceous follicle and prevent the pore from functioning correctly. If the pore is open, the comedone will be dark in appearance and is thus called a blackhead.

Closed Comedone (Whitehead)	Non-inflammatory comedone with a white center.
Papule	An inflammatory comedone that resembles a small red bump on the skin.
Pustule	An active infection of the skin that consists of dead skin cells and bacteria. These lesions are spherical in appearance and are filled with pus. Often reddish in color, pustules may be painful and will break open easily if scratched or bumped.

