9.1 Phase I

There are no predetermined criteria for discontinuation during Phase I. Subjects will be allowed to continue in the trial even if they do not achieve the goals of the two interventions and eventually receive the infertility treatment in Phase II. However each subject will have to complete the 16 week pretreatment period before receiving the Phase II treatments. Subjects can not be accelerated into Phase II.

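### Sections 1.8 and 10.9 disagree on the time variable of the weight-loss model, and the 10.9 version read literally leaves out the on-treatment Phase I weights

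*Combined protocol and SAP*

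**What the plan says.** Section 1.8 takes weight loss as its example of a secondary outcome for a linear mixed model, in which "the main independent variables will be treatment group, time, and their interaction", with the stratification factors as covariates. Section 10.9 describes what is plainly the same model, but for "weight loss or ultrasound parameters, a linear mixed-effects model will be fit where the main independent variables will be treatment arm, cycle number" (with an interaction term), again with site and baseline BMI. It adds that baseline value, age and prior drug exposure may be included in these secondary models.

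On timing, section 1.5 states: "The pretreatment intervention will last 16 weeks and is designed to promote a weight loss of approximately 7% of total body weight". Section 9.1 requires that "each subject will have to complete the 16 week pretreatment period before receiving the Phase II treatments". Section 7.2 lists weight at the randomization visit, at the three monthly visits ("Perform limited physical exam, including weight, waist circumference, and vital signs") and at week 16, and section 6.1 adds weekly home weights from the wireless scale. In Phase II, 7.2 lists a weight at the cycle 1 baseline visit, of which it says "This baseline visit will be performed at the start of Cycle 1 only", and at the end-of-Phase-2 visit. Section 7.3.2 says more generally that "Weight and waist circumference will be collected at each site visit".

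The primary model in 1.8 and 10.9 is a logistic regression on arm, site and baseline BMI. Age is not in it.

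**The concern.** An analyst cannot follow both sections. The 1.8 version can hold every weight from randomization onward. The 10.9 version can hold only weights that carry a cycle number, and the period designed to produce the weight loss has none.

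Two things would be lost. One is the record of weight while the intervention is being delivered. The other is the randomized comparison for this outcome: a woman who conceives in Phase I, which 6.1 encourages, or who leaves, and so never starts a cycle, is dropped because of something that happened after randomization.

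This matters because section 10.2 rests the design on the intensive arm losing weight while the standard arm holds it. If good birth outcome does not differ between arms, readers will first ask whether the arms separated on weight by week 16. The 10.9 model as worded does not answer that for all randomized women.

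**Working it through.** **Can cycle number cover Phase I?**

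- Section 7.2 uses cycle for Phase II stimulation cycles, up to three per woman.
- Section 9.1 lets none begin until the 16 weeks are complete.
- Menstrual cycles cannot stand in, because 7.2 schedules randomization and the week-16 visit without regard to cycle day.
- Section 10.9 also uses cycle number for ovulation rates, where it fits.

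**Which weights have an index under each version?**

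| Weight | 1.8 (time) | 10.9 (cycle number) |
|---|---|---|
| Randomization | yes | only as change-score baseline or covariate |
| Months 1, 2, 3 | yes | no |
| Week 16 | yes | no |
| Weekly home weights, Phase I | yes | no |
| Cycle 1 baseline | yes | yes, Phase II entrants only |
| Later Phase II weights | yes | where assignable to a cycle, Phase II entrants only |

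Section 6.1 says weight will be clamped in Phase II, so the weights that 10.9 keeps after cycle 1 mainly describe maintenance.

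**How many women might have no cycle?** FIT-PLESE gives no figure. For scale only, Table 5 of the predecessor PCOS trial has Phase 1 denominators 49 + 50 + 50 = 149 and Phase 2 denominators 44 + 44 + 43 = 131.

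- Not entering Phase 2: 149 - 131 = 18; 18/149 = 12.1% (Wilson 95% CI 7.8 to 18.3%).
- By arm: 5/49, 6/50, 7/50; chi-square 0.34 on 2 df, p = 0.85.
- Applied to 380 women: 0.121 x 380 = 46. An assumed range of 5% to 25% gives 19 to 95.

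**What might that do to the arm difference?** Illustration with that trial's Table 4 changes: -6 kg (lifestyle) and -1 kg (OCP), a 5.0 kg difference. Treat these as the changes among women who start a cycle, and let 12% never start.

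- Intensive non-starters lose 0 kg, standard arm unaffected: 0.88 x 6 = 5.28; 5.28 - 1 = 4.28; gap 5.00 - 4.28 = 0.72 kg.
- Same, but non-starters lose 3 kg: 5.28 + 0.36 - 1 = 4.64; gap 0.36 kg.
- Same, but non-starters lose 6 kg: gap 0.
- Non-starters at 0 kg in both arms: 5.28 - 0.88 = 4.40; gap 0.60 kg.

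**The primary sample size.** Two-sided 0.05, 80% power, 0.25 vs 0.40, mean 0.325: n = [1.960 x sqrt(2 x 0.325 x 0.675) + 0.842 x sqrt(0.25 x 0.75 + 0.40 x 0.60)]² / 0.15² = (1.298 + 0.550)² / 0.0225 = 151.9, so 152 per arm; 151.9/0.8 = 189.8, so 190. This reproduces Table 11. Weight does not enter it.

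**Age in the primary model (the separate improvement).** The documents give no age effect, so odds ratios per SD of age are assumed. Simulation used 12,000 trials per setting, marginal rates fixed at 0.25 and 0.40, 13 sites (assumed logit SD 0.3), an assumed BMI effect of -0.15 logit per SD, and a Wald test. Entries are percent power without and with age.

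| OR per SD | 152 per arm | 190 per arm | Conditional treatment OR |
|---|---|---|---|
| 1.0 | 81.9, 81.8 | 89.7, 89.6 | 2.00 |
| 0.8 | 81.8, 82.1 | 88.7, 88.9 | 2.01 |
| 0.7 | 81.7, 82.7 | 89.2, 89.9 | 2.04 |
| 0.6 | 81.6, 83.4 | 89.0, 90.4 | 2.08 |
| 0.5 | 81.7, 85.0 | 88.3, 91.1 | 2.14 |

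The last column comes from numerical integration over a normal age distribution with the marginal rates held fixed; the marginal odds ratio is (0.40/0.60)/(0.25/0.75) = 2.00.

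**The case against.** The best defence is that 10.9 is loosely worded and not a different plan. Its paragraph opens by speaking of observations repeated over time, one sentence covers weight and ultrasound together, and 1.8 already gives the workable version. That is plausible, but 10.9 is the detailed analysis section, and an analyst following it would fit cycle number.

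A reader might infer that 10.9 discards all information on Phase I weight loss. The documents do not support that. Baseline weight can enter through the change score or as a covariate, and for women who start treatment the cycle 1 weight, taken soon after week 16, roughly stands in for it. What is lost is the on-treatment course and the women who never start.

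The missing-data paragraph of 10.9 allows imputation and pattern-mixture models so that women with missing data can be included. This does not solve the problem: the Phase I weights are observed and simply have no index in the model.

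It is also fair that weight loss appears in none of the secondary-outcome lists (1.7, 2.2, 10.3.2) and only as an example in 1.8 and 10.9. Tertiary aim 1 in 2.3 relates a woman's own weight loss to ovulation and pregnancy, so it does not depend on the arm comparison. Both limit the importance of the point.

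On age, a fair objection is that the gain rests wholly on assumed effects, and that eligibility (18 to 40 years, with evidence of ovarian reserve) may weaken the association. That stands, and is why age is offered as an option.

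**Conclusion.** The contradiction is real and should be removed. As worded, 10.9 estimates the arm difference in weight only among women who entered Phase II, over a period when weight is to be held steady, and omits the month 1-3, week-16 and weekly home weights of Phase I.

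The size and sign of any bias are unknown. The 0 to 0.7 kg illustration borrows a 12% non-entry rate and weight changes from a different population and assumes how non-starters fared; it is not a forecast.

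Three stronger readings are not supported. The primary analysis is not compromised: weight is not the primary outcome, and 152 and 190 per arm reproduce exactly. The intent-to-treat statement in 10.9 is not breached, since it is made for the primary outcome. And the plan does not make age optional in the primary model: 1.8 and 10.9 fix that model at arm, site and baseline BMI, and age is optional only in the secondary mixed models and listed for the secondary logistic models.

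Adding age to the primary model is a separate improvement, not a correction. Section 3.2 ranks age above every other predictor of success in infertility treatment. Under assumed odds ratios of 0.8 to 0.5 per SD it adds roughly 0.3 to 3 points of power, with no material loss if age is unrelated, and the conditional odds ratio moves from 2.00 to about 2.01-2.14.

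**What to change.** In 10.9, separate weight from the per-cycle outcomes. Index weight by scheduled visit or week since randomization, in line with 1.8. Report the week-16 arm difference, using all randomized women with weights, and make baseline weight a fixed covariate instead of a possible one. It would help to state how weights after a Phase I conception are treated. Keep cycle number for the ultrasound and ovulation outcomes.

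Optionally, name age at randomization (continuous) beside site and baseline BMI in the primary logistic model in 1.8 and 10.9. Settle this before the analysis, because it changes the conditional odds ratio being reported; the arm proportions are reported as planned either way.

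The cost is wording in 1.8 and 10.9: no new data and no change in sample size.
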